#### **10. DATA**

**Will subjects be anonymous to the researcher?**

Subjects will not be anonymous to the researchers. As part of the consent process and verification of eligibility, subjects must provide their name, date of birth and other identifying information to members of the research team. However, identities will be kept confidential to the extent possible (see Confidentiality section below). De-identified data may be presented in abstract, poster, presentation, or published manuscript format.

**If subjects are identifiable, will their identities be kept confidential? (If yes, please specify how)**

Subject identities will be kept confidential by assigning each subject a number.

**How will data be stored and kept secure (specify data storage plans for both paper and electronic files. For guidance see <http://www.udel.edu/research/preparing/datastorage.html> )**

All data sheets will be stored in the subject's folder in a locked file cabinet. Encrypted electronic data will be stored in a database on a password protected UD managed server. Identifiable data will be shared between sites through this database. Paper copies of consent forms for each site will be stored on-site. Electronic copies of consents will be encrypted and placed on a UD managed password protected server.

**How long will data be stored?**

All de-identified data will be stored indefinitely and may be used in future research studies.

**Will data be destroyed?  YES  NO (if yes, please specify how the data will be destroyed)**

Data with identifying information will be saved until the project is complete or the data are published, whichever comes first and then the identifiable data will be destroyed. This will involve all electronic data being wiped from hard-drives and servers and all paper data being shredded. Raw de-identified data will be stored indefinitely and may be used in future related studies.

**Will the data be shared with anyone outside of the research team?  YES  NO**

These data will be used by the current investigative team, and then, in compliance with NIH policy, shared with others through the NICHD DASH repository so that additional analyses can be performed. Once the primary hypotheses of the current proposal are tested, all data will be

cleaned, de-identified, and be deposited in the DASH repository. To ensure that the identities of research subjects cannot be readily ascertained with the data, NICHD DASH will store only data that are without identifiers and coded. According to NICHS DASH requirements, before submitting the data to NICHD DASH, investigators must:

- a. Strip the data of individually identifying information according to:
  - o the standards set forth in the [HHS Regulations for the Protection of Human Subjects](#) and related guidance (which covers individually identifiable private information), and
  - o the [Health Insurance Portability and Accountability Act \(HIPAA\) Privacy Rule](#) (which covers protected health information); and
- b. Assign to the de-identified data random, unique codes.

#### **How will data be analyzed and reported?**

Appropriate statistical analysis of the primary (General Linear Mixed Modeling) and exploratory (Cox Proportional Hazards Model and a Generalized Estimating Equation) outcomes will be completed under the direction of the biostatistician on the project. The results will be reported to professionals interested in research via journals and presentations.

#### **11. CONFIDENTIALITY**

##### **Will participants be audiotaped, photographed or videotaped during this study?**

Individual subjects may be approached and asked to be photographed or videotaped for recruitment, educational or research purposes. A photo release form will be signed by participants prior to any photographs or videotape taken. Subjects will be told that this is an optional activity and not a requirement of participation. Photographs or video will have the face covered.

##### **How will subject identity be protected?**

All participants' identifying information will be stored in a locked file cabinet (paper forms) or on password-protected computers or servers (electronic forms) and will be utilized only by investigators on the protocol who have a specific need for the identifying information. All data collection sheets and all data will be de-identified and, instead, coded using a numerical system, the key to which will be maintained on a password-protected computer. These de-identified data and data collection sheets will also be stored in a locked file cabinet (paper forms) or on password-protected computers or servers (electronic forms) that are kept separate from the identifying information.

##### **Is there a Certificate of Confidentiality in place for this project? (If so, please provide a copy).**

There is no Certificate of Confidentiality in place for this project.

#### **12. CONFLICT OF INTEREST**

(For information on disclosure reporting see: <http://www.udel.edu/research/preparing/conflict.html> )

**Do you have a current conflict of interest disclosure form on file through UD Web forms? Yes**  
**Does this project involve a potential conflict of interest\*? NO**

\* As defined in the [University of Delaware's Policies and Procedures](#), a potential conflict of interest (COI) occurs

when there is a divergence between an individual's private interests and his or her professional obligations, such that an independent observer might reasonably question whether the individual's professional judgment, commitment, actions, or decisions could be influenced by considerations of personal gain, financial or otherwise.

If yes, please describe the nature of the interest:

### 13. **CONSENT and ASSENT**

X Consent forms will be used and are attached for review (see Consent Template under Forms and Templates in IRBNet)

Additionally, child assent forms will be used and are attached.

Waiver of Documentation of Consent (attach a consent script/information sheet with the signature block removed).

Waiver of Consent (Justify request for waiver)

### 14. **Other IRB Approval**

**Has this protocol been submitted to any other IRBs?** Not yet, but it will be submitted to the University of Pennsylvania and Christiana Care Health System IRBs.

### 15. **Supporting Documentation**

*Please list all additional documents uploaded to IRBNet in support of this application.*

Appendices which include IRBNet Protocol ID# 619037-1, entitled "Shared Pre-enrollment Process for Stroke Research Team Studies", that is referenced in this protocol, along with copies of specific clinical tests, screening questions and the inclusion/exclusion checklist for this protocol.

A separate Appendix is attached with the example DSMB charter.

### 4. Special Populations

Does this project involve any of the following:

Research on Children? **NO**

Research with Prisoners? **NO**

If yes, complete the Prisoners in Research Form and upload to IRBNet as supporting documentation

Research with Pregnant Women? **NO**

Research with any other vulnerable population (e.g. cognitively impaired, economically disadvantaged, etc.)? please describe **NO**

5. **RESEARCH ABSTRACT** Please provide a brief description in LAY language (understandable to an 8th grade student) of the aims of this project.

The **overarching goal** of this research is to develop interventions that improve the overall health and quality of life of individuals post-stroke. As a group, stroke survivors are more physically inactive than even the most sedentary older adults. Lack of physical activity has serious consequences in persons with stroke, including an increased risk of recurrent stroke, developing other diseases and mortality. Current rehabilitation interventions do little to improve real-world walking activity after stroke, suggesting that simply improving walking capacity is not sufficient for improving daily physical activity after stroke. Rather, we hypothesize that the combination of a fast walking intervention that improves walking capacity, with a step activity monitoring program that facilitates translation of gains from the clinic to the “real-world”, would generate greater improvements in real world walking activity than with either intervention alone. Data from our lab provides support for this hypothesis; however, it suggests that the greater efficacy of combining the 2 interventions depends on a participant’s initial walking activity. Thus, *we do not expect that one intervention will be superior to the others for all participants*, but rather that the combined intervention will be superior for those with low levels of baseline walking activity, speed and endurance. The **specific objective** of this research is to test *whether and for whom* combining fast walking training with a step activity monitoring program

(FAST+SAM) is superior in improving real-world walking activity compared to fast walking training alone (FAST) or a step activity monitoring and feedback program alone (SAM) in those with chronic stroke. Using a randomized controlled experimental design, 225 chronic (> 6 months) stroke survivors, will complete approximately 12 weeks (goal of 36 sessions) of fast walking training (FAST), a step activity monitoring program (SAM) or a fast walking training + step activity monitoring program (FAST+SAM). The primary (steps per day), secondary (self-selected and fastest walking speed, walking endurance, oxygen consumption) and exploratory (vascular events, blood lipids, glucose, blood pressure) outcomes will be assessed by blinded evaluators prior to initiating treatment, after the last treatment and at a 6 and 12 month follow-up. Moderation of specific intervention outcomes by baseline characteristics will be evaluated to determine *for whom* the interventions are effective. Following completion of this study, we will not only understand the efficacy of the interventions and the individuals for which they are effective, we will have the necessary information to design a study investigating the secondary prevention benefits of improved physical activity post-stroke. This study is, therefore, an important step in the development of secondary prevention guidelines for persons with stroke.

[figure not shown]
## 6. PROCEDURES

750 adults with a past history of stroke will be recruited to participate in the study. The study will take place at 4 sites, the University of Delaware (UD), the University of Pennsylvania (UPenn), Christiana Care Health System (CCHS) and Indiana University (IU). We anticipate 225 subjects will complete the study. The number recruited at each study site will be flexible as recruitment varies across sites. Subject numbers are monitored on an ongoing basis through the REDCap database. See information regarding recruitment methods in #7 below. All testing and training (intervention) sessions will occur at IU, UPenn and UD, while only training sessions will occur at CCHS with testing of CCHS subjects occurring at UD. Data collection sessions at the University of Pennsylvania were ended as of July 2020, but analysis of data collected at that site will continue through the end of the project.

We may recruit participants from the University of Delaware Stroke Research Registry (IRB# 1642798). Please see attached Study Approval Letter. Participants recruited through other means will be offered the opportunity to enroll in the Stroke Research Registry when they consent to this study. Lab members will be instructed to emphasize that enrolling in the Registry is completely voluntary and the participant's choice to enroll or not has no effect on their participation in this study or any other studies conducted at the University of Delaware.

Regardless of recruitment method, during the initial phone call or email a member of the research team will describe the purpose and general procedures of the study. We will explain what to expect and the potential risks and benefits of participation. We will also inform the potential participant that joining the study is completely voluntary and that he/she is free to reconsider or stop participation at any time. If the potential participant expresses interest in agreeing to join, we will then proceed with a series of screening questions to determine if the person might be eligible (see Appendices). For subjects that do not appear to be eligible, screening forms will be destroyed. No additional documentation (e.g.- consent forms, HIPPA forms) will be handled by UD in regards to UPenn or IU subjects.

Once potential eligibility for a participant is determined, subjects will be scheduled for PRE Clinical Baseline Testing. During the PRE Clinical Baseline Testing, subjects will fill out the PROWALKS Consent form, the Stroke Registry Consent form and the PROWALKS Medical Clearance form. The medical clearance must be completed prior to participating in the submaximal stress test. Medical clearance can be given verbally to a Stroke Team member following discussion with the provider. The medical clearance form will be noted to indicate the information that was provided verbally, along with the date of the receipt of that information, the provider's name, and the signature of the person obtaining the information. If we become aware of a new medical issue with a participant that would likely impact their participation in future studies we will relay this information for inclusion in the Stroke Research Registry (IRBNet Protocol ID# 1642798, Stroke Research Registry) so that other investigators potentially interested in recruiting this person into a different study are aware.

At the time of the first evaluation session, a member of the research team will first review the informed consent documents in detail with the potential participant. This will include a description of the study purpose and procedures, inclusion and exclusion criteria, the potential risks and benefits of participating, alternatives to participating, subjects' rights (such as withdrawal from the study, etc.) and compensation. The participant will be encouraged to ask questions and express concerns at any time during the consenting procedure or thereafter. If the participant agrees to be in the study, he/she will be asked to sign the informed consent document.

The figure illustrates the basic study design. Each evaluation session will last 1-3 hours and each training (intervention) session will last approximately 1 hour. There are a total of 8-12 evaluation sessions and 36 intervention sessions.

## **Testing Procedures**

***Baseline evaluation session.*** Subjects will undergo a brief battery of clinical assessments conducted by a trained member of the research team. Clinical assessments will include collection of medication and co-morbidity information, blood pressure, heart rate and body mass index, the 10 meter walk test, the 6 minute walk test, the Activities Specific Balance Confidence scale (ABC), the Patient Health Questionnaire nine-item depression scale (PHQ-9), and the Montreal Cognitive Assessment (MoCA) (see Appendices). In addition, subjects will be provided with a Stepwatch Activity Monitor and/or Fitbit activity monitor and instructed in its wear and use. Subjects will wear the monitor for 1 week. Following this baseline evaluation session and the 1 week step monitoring, the inclusion criteria of walking speed between 0.3 and 1.0 m/s and steps/day less than 8000, can be evaluated and continued eligibility confirmed. If subjects do not meet these criteria after evaluation, they will be withdrawn from the study.

If any subject scores  $\geq 5$  on the PHQ-9, they will be informed of their score and advised to discuss this with their primary physician. In addition, for any participant endorsing suicidal ideation on one or more test items on PHQ-9, (1) we will notify the physician and (2) we will give the participant the telephone number for Crisis Intervention Services of Northern Delaware ([[contact]]([contact]) or [[contact]]([contact])) which is staffed 24 hours/day, 7 days a week, to whom they can reach out if they feel desperate, hopeless and/or at risk for suicide. This is standard procedure for clients in the Physical Therapy Clinic.

Symptom limited graded exercise test. Prior to beginning the intervention, all subjects will undergo a symptom limited graded exercise test (GXT) on a motorized treadmill in the Nurse Managed Health Center (NMHC) under the supervision of a nurse practitioner and an exercise physiologist. During the GXT a 12 lead electrocardiogram and breath by breath analysis of oxygen consumption with a metabolic cart will be recorded. The results of the test will be reviewed by a cardiologist for abnormal responses that would prevent the subject from safe participation.

Subjects will have up to 5 ml of blood drawn by a trained practitioner in the NHMC for measurement of blood lipids and glucose at each of the testing time points (baseline, post-intervention and 6 and 12 month follow-up evaluation sessions).

Post-intervention and follow-up evaluations. Post, 6 and 12 month evaluation sessions will be identical to the baseline evaluation including the graded exercise test for the purposes of measuring changes in oxygen consumption that may have occurred with the intervention and measurement of blood lipids and glucose.

In order to examine the potential secondary prevention benefits of the intervention, at the 6 and 12 month follow-up appointment subjects will be asked about major adverse cardiovascular and cerebrovascular events (MACCE); specifically if they have had: recurrent stroke, myocardial infarction, unstable angina requiring hospitalization or peripheral artery event and the date of that event. This data will be confirmed for accuracy through contact with the subject's physician. Phone follow-up at 2 years will be completed for subjects enrolled in the first 2 years of the study to collect longer term follow-up data on these events. Information received from subjects will be confirmed by their physician (see Appendices). If subjects have any of these events during the course of the study, they will be withdrawn from all testing and training, except we will continue to track them for MACCE.

Decisions will be made regarding withdrawing subjects at 6 and 12 months by gathering medical record information as needed for subjects who report changes in their health history. Self-reported and non-physical measures may still be collected at 6 and 12 month time points even if they are not able to perform physical testing.

In addition to the 6 and 12 month follow-up, subjects will be contacted by the Stroke Studies Coordinator at UD at 4.5, and 9 months post baseline testing to check in as a means to improve subject retention. Subjects will be told that we are calling to check in. We will ask them if anything has changed since their last visit/phone call, including address, contact information, physician. Any changes in this information will be updated in the database.

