## **Testing Procedures**

**Baseline evaluation session.** Subjects will undergo a brief battery of clinical assessments conducted by a trained member of the research team. Clinical assessments will include collection of medication and co-morbidity information, blood pressure, heart rate and body mass index, the 10 meter walk test, the 6 minute walk test, the Activities Specific Balance Confidence scale (ABC), the Patient Health Questionnaire nine-item depression scale (PHQ-9), and the Montreal Cognitive Assessment (MoCA) (see Appendices). In addition, subjects will be provided with a Fitbit activity monitor and instructed in its wear and use. Subjects will wear the monitor for 1 week. Following this baseline evaluation session and the 1 week step monitoring, the inclusion criteria of walking speed less than 1.0 m/s and steps/day less than 8000, can be evaluated and continued eligibility confirmed. If subjects do not meet these criteria after evaluation, they will be withdrawn from the study.

If any subject scores  $\geq 5$  on the PHQ-9, they will be informed of their score and advised to discuss this with their primary physician. In addition, for any participant endorsing suicidal ideation on one or more test items on PHQ-9, (1) we will notify the physician and (2) we will give the participant the telephone number for Crisis Intervention Services of Northern Delaware ([[contact]]([contact]) or [[contact]]([contact])) which is staffed 24 hours/day, 7 days a week, to whom they can reach out if they feel desperate, hopeless and/or at risk for suicide. This is standard procedure for clients in the Physical Therapy Clinic.

**Symptom limited graded exercise test.** Prior to beginning the intervention, all subjects will undergo a symptom limited graded exercise test (GXT) on a motorized treadmill in the Nurse Managed Health Center (NMHC) under the supervision of a nurse practitioner and an exercise physiologist. During the GXT a 12 lead electrocardiogram and breath by breath analysis of oxygen consumption with a metabolic cart will be recorded. The results of the test will be reviewed by a cardiologist for abnormal responses that would prevent the subject from safe participation.

Subjects will also have their blood drawn by a trained practitioner in the NHMC for measurement of blood lipids and glucose.

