During training, the RPE will be assessed every 2 minutes and heart rate will be continuously monitored. Blood pressure is tested prior to the initiation of any activity. It is also checked at the Research PT's discretion any time walking is stopped, including rest breaks, at the end of treadmill walking (prior to the start of over ground walking) and following over ground walking. For all sessions, the guidelines set forth by the American College of Sports Medicine for individuals in phase III or IV of cardiac rehabilitation will be followed. Based on these guidelines, we have developed session termination criteria. A session will be terminated if any of the following occur:

- Drop in Systolic blood pressure of  $\geq 10$ mmHg from baseline (resting for that day) despite increase in workload
- Hypertensive response with a systolic blood pressure  $>240$  mmHg and diastolic blood pressure  $>110$
- Presence of nervous system symptoms: ataxia, dizziness, or near syncope
- Any chest pain or angina symptoms
- Signs of poor perfusion cyanosis or pallor
- Excessive fatigue, excessive shortness of breath, leg cramps, claudication

If any of the above occurs, the subject's physician will be contacted and informed of the subject's response to the activity. Subjects can also terminate any session or training bout by stating their desire to stop.

Step activity monitoring program. Subjects in the SAM and FAST+SAM groups will participate in the step activity monitoring program and will be provided with a Stepwatch Activity Monitor and/or Fitbit. If the device is lost or damaged, it will be replaced to allow continued participation in the step activity monitoring program. Baseline step activity data for subjects in the FAST+SAM and SAM groups will be used to categorize and assign step activity goals. It is important to note that goals are set not based on an absolute number for all subjects, but rather individually, based on their own baseline walking. Goals are advanced based on subject achievement of previous goals. For subjects in the FAST+SAM group, step activity data is reviewed at each treadmill training session and used to determine and promote goal achievement. Subjects in the SAM group will visit the clinic 3x/week for this review. Step activity data in the interim days between sessions will reviewed and used to assist subjects in

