understanding how much walking activity they performed during certain daily activities, like walking to the mailbox or walking laps around their home, and how that added to their total steps per day. Subjects are also advised of how their steps per day related to goal achievement; a discussion of individualized ideas to increase activity and of any barriers and how to overcome those barriers. These discussions have been shown to be critical for the success of a step activity monitoring program.

Subjects in the FAST group will be instructed not to begin the use of a step monitor during the study.

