# Summary of protocol changes

## Summary of protocol changes

Approval date	Description of protocol changes
3/23/2016	Initial approval
5/1/2017	To exclude individuals who walk at <0.3m/s (due to limitations of Fitbit sensitivity); to ensure consistency in language describing training phase in protocol and consent form
10/16/2018	To add IU as an evaluation and training site
9/28/2020	To add language to consent form to reflect that while risk of COVID-19 exposure will be minimized, the risk of exposure cannot be completely eliminated

**Original statistical analysis plan  
(excerpted from original IRB protocol  
(2016), NIH grant application (2014), and  
published protocol (2018)**

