## General data management & analysis

Encrypted electronic files that connect subject identities to their subject code will be stored in a database on a password protected server. Paper copies of consent forms for each site will be stored on-site. Paper copies of the screening form for subjects that sign the Informed Consent are also stored at each site.

The Biostatistician running analyses is blinded to group assignment. An “intent to treat” analysis will be performed. To ensure that the randomization worked, potential covariates (e.g. age, time since stroke, cognition) will be compared between groups using t-tests and  $\chi^2$  tests. If a covariate is significantly different between groups, this will be an indication that the groups are not balanced and the covariate will be included in the models. The alpha is set at 0.05 for primary analyses and .01 for secondary analyses.

Aims 1 & 2 will be tested using General Linear Mixed Models (GLMM). To compare the efficacy of the FAST+SAM, FAST and SAM interventions for improving real-world walking activity in chronic stroke survivors and to determine for whom the interventions are most effective General Linear Mixed Models (GLMM) will be developed. All model assumptions will be tested (including linearity, normality, homoscedasticity, and multicollinearity). Outliers and influential cases will be screened for and removed. Violations of the assumptions will be remedied using transformations or a Generalized Linear Model. Post-hoc tests in the GLMMs will use Bonferroni adjustment and for the regression models post-hoc probing of interactions will be done using simple slopes method.

For the GLMMs, the covariance structure will be chosen using nested model comparisons. The regression models also have the assumptions of homoscedasticity and multicollinearity, which will be tested using the Breusch-Pagan test, and by examining the condition index and variance inflation factor, respectively. To eliminate ignorable collinearity caused by the inclusion of interaction terms, continuous variables will be centered before being entered into the models. Site differences will also be tested, and if differences exist, will be included in the model to control for them.

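### Does allowing a StepWatch and/or a Fitbit, with no written one-device rule, bias the change in steps/day?

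*Combined protocol and SAP*

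**What the plan says.** In the original protocol (section 6, Testing Procedures, baseline evaluation) "subjects will be provided with a Fitbit activity monitor and instructed in its wear and use". The final protocol replaces this with the wider wording: "subjects will be provided with a Stepwatch Activity Monitor and/or Fitbit activity monitor and instructed in its wear and use". It then refers to the monitor in the singular, worn for one week. For the later visits, both versions say "Post, 6 and 12 month evaluation sessions will be identical to the baseline evaluation".

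Under Intervention Procedures, the step activity programme in the SAM and FAST+SAM arms also uses a StepWatch and/or a Fitbit: "If the device is lost or damaged, it will be replaced to allow continued participation in the step activity monitoring program". By contrast, "Subjects in the FAST group will be instructed not to begin the use of a step monitor during the study".

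The Summary of protocol changes mentions a device once, in the May 2017 entry that excludes people walking below 0.3 m/s "due to limitations of Fitbit sensitivity". It lists no change of device.

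The SAP (Expected outcomes and aim specific analysis, Aim 1) takes steps/day at each time point as a one-week average and names no device. H1.1 tests the change from before to after training, averaged over the three groups. Under General data management & analysis, baseline covariates enter the model "If a covariate is significantly different between groups", and "Site differences will also be tested, and if differences exist, will be included in the model to control for them".

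**The concern.** The permitted instruments for the primary outcome widened during the trial, and the SAP did not follow. If both monitors are worn, no visible text says which count is the outcome. A participant could in principle have a Fitbit count at baseline and a StepWatch count at 12 months. If the two devices count differently, that difference becomes part of the participant's change in steps/day.

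Randomization does not protect a change over time. H1.1 is such a change, and so is the improvement of at least 1700 steps/day in FAST+SAM that the SAP's power section calls worth further study. Adjusting for site or for unbalanced baseline covariates cannot remove a shift that arises within a participant between visits. Two of the three arms also handle monitors during treatment and the third does not, which raises the question of whether device changes could differ by arm.

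**Working it through.** **Step 1. What the text directs.** Baseline: one monitor, worn for a week, StepWatch and/or Fitbit. Post, 6 and 12 months: sessions identical to baseline. For one participant, the natural reading is that the same measurement is repeated. The text does not lock the device, but it directs nobody to change it. The May 2017 exclusion rests on what a Fitbit can detect, and the final protocol keeps that speed limit. This fits continued use of the Fitbit, though it does not prove it. If the choice of device varied by site, it would be constant within a participant and a fixed offset would cancel from the change.

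**Step 2. The plan's own figures** (SAP, Power analysis & sample size): SD 2,500, correlation 0.50, 75 per arm, 225 in total.

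- SD of change = 2500 × √(2 × (1 − 0.50)) = 2500
- SE of the pooled change = 2500/√225 = 166.7
- SE of the change in one arm = 2500/√75 = 288.7
- SE of a between-arm difference = 2500 × √(2/75) = 408.2
- Planned contrast = 1700 − 250 = 1450. Two-sided power at 0.05 = Φ(1450/408.2 − 1.96) = Φ(1.59) = 0.944, or 0.942 with the t distribution on 148 df.

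The stated power above 0.90 is reproduced. This applies the low-baseline figures to whole arms, because the SAP gives no others for this contrast. It does not depend on the device.

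**Step 3. Size of a device shift.** Let d be the difference in count per change of device, and p the net share changing in one direction (changes one way minus changes the other way). The shift in the mean change is p × d. If either is zero, the shift is zero. The documents give neither, so both are assumed: d from 200 (5% of 4,000) to 900 (20% of 4,500), and p from 0 to 50%.

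| p | shift at d = 200 | shift at d = 900 | in SEs of 166.7 |
|---|---|---|---|
| 0 | 0 | 0 | 0 |
| 5% | 10 | 45 | 0.06 to 0.27 |
| 25% | 50 | 225 | 0.30 to 1.35 |
| 50% | 100 | 450 | 0.60 to 2.70 |

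**Step 4. H1.1.** The planning changes for FAST, SAM and FAST+SAM average (250 + 1100 + 1700)/3 = 1017, which is 1017/166.7 = 6.1 SE. After a shift of 450 against the effect, (1017 − 450)/166.7 = 3.4 SE remain. With the SAP's other figure for fast walking alone (about 1000), the average is 1267, or 7.6 SE, and (1267 − 450)/166.7 = 4.9 SE remain. Either way the test stays well beyond 1.96.

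**Step 5. Between-arm contrasts.** An equal shift in every arm cancels. If the shift fell wholly in one arm and reduced the contrast:

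- 200 steps/day: Φ((1450 − 200)/408.2 − 1.96) = Φ(1.10) = 0.865
- 400 steps/day: Φ((1450 − 400)/408.2 − 1.96) = Φ(0.61) = 0.73

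With no true difference, the type I error would be 7.8% and 16.5% respectively. A one-arm shift of 400 needs, for instance, half of that arm changing the same way with d = 800.

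**Step 6. What a written rule would alter.** It would set p to 0. Sample size and planned power stay as they are.

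**The case for a change.** The strongest reply is that a session identical to baseline inherits the and/or. A participant who moved from a Fitbit to a StepWatch would still comply with the text, and someone enrolled under the original protocol could be followed up under the final one. A changeover on a calendar date would catch more 12-month intervals than 12-week ones. The robustness in Step 4 also relies on the planning effects being real. With no true change over time, a pooled shift of 200 would raise the false-positive rate of H1.1 from 5% to 22%, and a shift of 400 would raise it to 67%. Recording the device and tabulating it by visit would cost little.

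Part of this stands. The text does not lock the device, and if changes ran one way the estimated within-group change would move, including the FAST+SAM figure compared with 1700: a shift of 450 is 450/288.7 = 1.6 SE in one arm. The rest depends on facts not in evidence. The change log shows no changeover. It is a summary and so not conclusive, but no changeover date or enrolment period is given from which a share of affected participants could be worked out. Changes in both directions mostly add noise. The 1700 figure supports the sample size, and no test under Aim 1 uses it as a threshold. The replacement provision and the instruction to the FAST arm concern monitors in treatment and daily life; they do not show that the outcome week was measured differently by arm. The SAP is an excerpt and the appendices were not supplied, so a device rule may exist there.

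**Conclusion.** The concern identifies an unwritten detail and does not demonstrate a wrong result. Bias needs participants to change device mainly in one direction and the devices to count differently, and the documents show neither. Repeating the baseline session most naturally keeps a participant on the same device. An analyst computing change in steps/day would take both counts from the same device, and would look at device by visit and arm before interpreting the change.

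Under the assumed ranges the shift in the pooled mean change runs from 0 to 450 steps/day (0 to 2.7 SE), with the top of the range requiring half of all participants to change in the same direction at a 20% difference. Given the planning effects, H1.1 holds even there. The between-arm comparison, which is the trial's stated objective, is untouched unless device changes differ by arm. The conclusion rests on the SAP's SD, correlation and group sizes, and on the reading that follow-up repeats the baseline measurement. Evidence of frequent one-way changes, or of changes that differed by arm, would reopen the question. As the plan stands, no change is called for.
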